Very rapidly the virus emerged as pandemic. Now it is dominating the lives of every people of this universe. Till date **75,53,182 confirmed cases** of COVID-19, including **4,23,349 deaths**, reported to WHO. In Bangladesh cases as well as the death tolls are also increasing exponentially (84,379 cases and 1,139 death).

Management of the COVID-19 relies on mainly supportive care and oxygen supplementation via non-invasive or mechanical ventilation in critical cases. Patients who are critically ill may also require vasopressor support and antibiotics for secondary bacterial infections.

There is no vaccine or highly effective antiviral drugs for COVID-19. Currently there is a tremendous effort around the world to develop effective preventive and therapeutic treatment for this disease.

World Health Organization has launched a non-blinded clinical trial (SOLIDARITY) to evaluate four candidate treatments (remdesivir, lopinavir/ritonavir, lopinavir/ritonavir/interferon beta-1a, and chloroquine or hydroxychloroquine) versus standard of care in 18 countries worldwide. RECOVERY trial one of the largest trials to see the efficacy and safety of hydroxychloroquine revealed that they are no clear cut clinical benefit for COVID-19. Other drugs in the SOLIDARTY trial are quite expensive for resource limited countries like Bangladesh.

Study Published in the American Journal of Tropical Medicine advocates further research into Ivermectin for COVID-19 Treatment. The spotlight on Ivermectin was brought by Australian researchers from Monash University who demonstrated its efficacy against the SARS-CoV-2 coronavirus in vitro studies.

In a recent international, multicenter, propensity-score matched case- controlled study using prospectively collected data on patients diagnosed with COVID 19 by Patel et al, observed substantial benefit using Ivermectin over standard care.

In different study Doxycycline also showed promising results in treatment of COVID 19 infection. It is highly lipophilic antibiotics that are known to chelate zinc component of matrix metalloproteinases (MMP). Corona viruses are known to rely heavily of MMPs for survival, cell infiltration and replication. It also has an anti-inflammatory effect which might be effective in combating cytokine storm of Covid-19 infection.

So it have been planned to conduct an experimental clinical trial using combination of ivermectin and doxycycline for treatment of COVID 19 along with the other standard care. It would be a randomized double blind placebo controlled Trial. The study would be conducted on 200 confirmed cases of Covid- 19. Another 200 patients will receive placebo.

The primary outcome would be the Days required for the Clinical improvement of the patients from the day of randomization.

Data will be analyzed using SPSS 20. Unpaired t-test would be used for testing quantitative data and for testing qualitative data two sample z- test would be used. For the comparison between two groups Hazard ratio, Kaplan-Meire curve, binary logistic regression would be used to see the outcome. Result of the study and statistical analysis will be presented by tables, figures, graphs, diagrams, charts and photographs. All these will have own legends (i.e. title) and will be serially numbered. Discussion will be done on the basis of result obtained from the study and comparing with similar studies done at home and abroad. Summarization will be drawn after discussion. Conclusion will be drawn depending upon the results and discussion.

PART - D

INTRODUCTION

On 31 December 2019, the World Health Organization (WHO) was formally notified about a cluster of cases of pneumonia in Wuhan City¹. On 7 January the causative virus was isolated and its genome sequence was shared on 12 January. The cause of the severe acute respiratory syndrome that became known as COVID-19 was a novel corona virus, SARS-CoV-2². The virus Spread quickly through out the universe in quick succession. The World Health Organization (WHO) on March 11, 2020, has declared the novel Corona virus (COVID-19) outbreak a global pandemic³.

Phylogenetic analysis suggests that SARS-CoV-2 originated in animals, probably bats, and was transmitted to other animals before crossing into humans at the Huanan wet market in Wuhan City⁴⁻⁵. It was the year 1918, when a new flu pandemic launched worldwide The pandemic infected 3% to 5% percent of the world's population including remote Pacific islands and the Arctic. The Life expectancy dropped by about 12 years⁶. The fatal casualties of the diseased had reached the number of the fifty million victims⁷.

That dreadful experience might be compared with the recent ongoing pandemic. By 13 june 2020, there have been 75,53,182 confirmed cases of COVID-19, including 4,23,349 deaths, reported to WHO⁸. Most of the countries of the word are in strict lockdown state. Now it is dominating the lives of every people of this universe. The Economy of the world also constricted. In Bangladesh cases as well as the death tolls are also increasing exponentially. Our Economy is also shrinking day by day.

While the clinical presentation of COVID-19 ranges from asymptomatic to fulminant and fatal, severe cases of infection can develop pneumonia, acute respiratory distress syndrome, sepsis and/or multiple organ failure which are not unique to coronavirus⁹.

Death is due to pneumonia and possibly hyper-inflammation associated with cytokine storm syndrome¹⁰.

Management of the COVID-19 relies on mainly supportive care. Approximately 14% of the Covid-19 patients develop severe disease that requires hospitalization and oxygen support, and 5% require admission to an intensive care unit¹¹.

There is no vaccine or specific antiviral drug for COVID-19 for which the people of the world are craving.

Worldwide the scientific community has focused on developing and/or repurposing medicines that can target SARS-Cov 2 and help control the pandemic of COVID-19.

Repurposing currently available medicines against COVID-19 has led to the development of hundreds of trials worldwide. Therapeutics under investigation includes various antiviral and immunomodulatory medicines¹².

Table: 1 All drugs used for COVID-19 in vitro lab and in vivo (clinical) human studies published from January 2020¹³.

Name of the Drug	Name of the Drug	Name of the drug
Meplazumab(monoclonal antibody)	Darunavir(antiviral)	Umifenovir/arithidol(antiviral).
Ivermectin	Nelfinavir(antiviral)	Lopinavir/ritonavir(LPVR)protease inhibitor
Siltuximab(monoclonal antibody).	Remdesivir(antiviral)	Interferon-alpha α
Danoprevir(antiviral)	Corticosteroids .	Interferon-beta β .
Tocilizumab/IL-6(monoclonal antibody).	Chloroquine/hydroxychloroquine	Heparin
Favipiravir(antiviral)	Convalescent Plasma	α -Lipoic acid

Many studies carried out independently in small group of people but there is a risk that the trials will lack statistical strength.

World Health Organization has launched a nonblinded clinical trial (SOLIDARITY) to evaluate four candidate treatments (remdesivir, lopinavir/ritonavir, lopinavir/ritonavir/interferon beta-1a, and chloroquine or hydroxychloroquine) versus standard of care in 18 countries worldwide¹⁴.

Recently a publication in lancet journal claimed that they were unable to confirm a benefit of hydroxychloroquine or chloroquine, when used alone or with a macrolide, on in-hospital outcomes for COVID-19. Each of these drug regimens was associated with decreased in-hospital survival and an increased frequency of ventricular arrhythmias when used for treatment of COVID-19. The Findings were controversial.

Other drugs in the SOLIDARTY trial are quite expensive as well as toxic for resource limited countries like ours. Study Published in the American Journal of Tropical Medicine advocates further research into Ivermectin for COVID-19 Treatment. It could emerge as a good drug candidate. It is cheap and less toxic. Dosing regimen is also simple.

The spotlight on Ivermectin was brought by Australian researchers from Monash University who demonstrated its efficacy against the SARS-CoV-2 coronavirus in vitro studies¹⁶.

Ivermectin has a broad spectrum antiviral activity. Recently it is found to be effective to

combat infections of RNA viruses like human immunodeficiency virus (HIV)-1, influenza, west nile virus , Zika virus and dengue virus(DENV)¹⁷.

Caly L et al demonstrate ivermectin has antiviral action against the SARS-CoV-2 clinical isolate *in vitro*, with a single dose able to control viral replication within 24–48 h in their system¹⁶.

Importin (IMP) $\alpha/\beta 130$ is a heterodimer that binds to the SARS-CoV-2 cargo protein and moves it into the nucleus which reduces the host cell antiviral response. Ivermectin destabilizes the Imp $\alpha/\beta 1$ heterodimer, prevents it from viral protein binding and thus from entering the nucleus.^{16, 17}

Ivermectin has an established safety profile for human use although there is not enough evidence to make conclusions about the safety profile in pregnancy¹⁸.

However, the *in vivo* antiviral potential of ivermectin has only been reported against the pseudorabies virus¹⁹ and parvoviruses²⁰.

Considering the promising result of the *in vitro* study, the clinical benefit of ivermectin therapy was evaluated in an observational registry-based study involving critically ill SARS-CoV-2-infected patients. Treatment with ivermectin at a dose of 150 $\mu\text{g/kg}$ was found to be associated with a lower mortality rate and reduced healthcare resource use²¹

The clinical efficacy and utility of ivermectin in SARS-CoV-2-infected patients are unpredictable at this stage, as we are dealing with a completely novel virus.

The exact mechanism behind ivermectin is still under investigation but studies have found that a single treatment of ivermectin in a COVID-19 patient can cause the effect of a ~5000-fold reduction in viral RNA at 48 hours^{16,22}. Due to an immensely significant decrease in viral load with just one dose, ivermectin holds a significant amount of promise and thus, warrants further investigation in humans.

In a recent international, multicenter, propensity-score matched case- controlled study using prospectively collected data on patients diagnosed with COVID 19 by Patel et al, observed substantial benefit using Ivermectin over standard care¹⁶. They found that fewer patients died in the ivermectin group (7.3 versus 21.3 percent) and overall death rates were lower with ivermectin (1.4 versus 8.4 percent).

Tetracyclines are antibiotics that are generally well-tolerated and widely available. They are generally used as broad spectrum antibiotics to treat different bacterial diseases as well as some atypical infection²³.

However, several authors have suggested they may be effective against different viruses as well. In a recent article, Mohit Sochi and Mahiyar Etminan , have suggested that they may be effective against COVID 19²⁴.

Tetracyclines are highly lipophilic antibiotics that are known to chelate zinc component of matrix metalloproteases(MMP)²⁵. Corona viruses are known to rely heavily of

MMPs for survival, cell infiltration and replication, many of which have zinc as part of their MMP complex²⁶. It may be possible that zinc chelating properties of tetracyclines may aid in inhibition of COVID 19 infection in humans. Some in vitro studies also suggested that tetracyclines may inhibit RNA replication on positive sense single stranded RNA viruses, like COVID 19.

Second, tetracyclines have well known anti-inflammatory effects. The anti-inflammatory mechanism of tetracyclines is complex and not fully understood. However, it probably involves inactivation of MMPs, serine proteases and decrease production of inflammatory cytokines such as TNF-alpha, interleukin beta and IL-6²⁷. It has been suggested that cytokines play an important role in the pathogenesis of COVID 19 including exacerbation of lung damage^{28,29}. Several authors have suggested that tetracyclines may be used to treat inflammatory disorders including those caused by Corona viruses.

Third, as they are highly lipophilic drugs, tetracycline has good tissue penetration in the lungs. This, along with their anti-inflammatory properties, might allow them to inhibit viral replication in the lung and reduce lung damage. The recommendation of using tetracyclines as treatment for Corona virus was previously suggested given that chemically modified tetracycline can prevent septic shock induced by ARDS³⁰.

Based on the evidences, Mohit Sodhi et Al strongly urged international research groups to consider investigating the potential therapeutic efficacy of tetracycline in treating COVID 19.

Compared with the original tetracycline, the synthetics, including minocycline and doxycycline, show a better pharmacokinetic profile than the first-generation tetracyclines when used orally, being rapidly and completely absorbed, even in elderly populations, with a longer half-life and excellent tissue penetration, with almost complete bioavailability³¹

The rationale of using combination of ivermectin and doxycycline for treatment of COVID 19 is based on their antiviral and anti-inflammatory properties. Since the two drugs have different mode of action, their synergistic effect would be of value to contain the viral infection by targeting different sites of the pathogenesis of the disease.

2. OBJECTIVES:

General objectives:

To observe the benefit (clinical and microbiological) of Ivermectin and Doxycycline in Confirmed Covid 19 cases.

Specific objectives:

1. To observe the clinical outcome in trial group and the placebo group.
2. To observe the duration require for the recovery in the trial and placebo group
3. To compare the outcome between the two groups.

3. RATIONALE:

Covid-19 is an emergent pandemic, threatens the life of millions of the people throughout the globe. There is increasing effort of the scientist to unveil a remedy of covid-19. Still it is unsuccessful. At present there is no other alternative other than experimenting the existent drug against the virus. There are several trials going throughout the globe. Among them Ivermectin showed good efficacy in vitro trial. Some clinical trial also proved it beneficial. The Doxycycline also has some anti-viral role with its prominent anti-inflammatory role. Synergistic action of the two drugs might be proved some benefit in clinical trial. As both drugs are cheap and less toxic, if it does, it would be the blessing for the poor people of the globe.

4. METHODOLOGY:

Study type: Interventional Clinical trial

Estimated enrollment: 200 participants per group

For superior trial, the formula is:

$$N = \frac{1}{2} \times \left(\frac{Z_{\frac{\alpha}{2}} + Z_{\beta}}{\arcsin \sqrt{p} - \arcsin \sqrt{P_0}} \right)^2$$

N=size per group; p=the response rate of standard treatment group; p₀= the response rate of new drug treatment group; z_x= the standard normal deviate for a one or two sided x; d=

the real difference between two treatment effect; δ_0 = a clinically acceptable margin; S^2 = Pooled standard deviation of both comparison groups.

All parameters were assumed as follows: $p = 0.40$; $p_0 = 0.58$; $\alpha = 0.05$; $\beta = 0.20$; $\delta = 0.18$; $\delta_0 = 0.10$.

$$N_{\text{statistical superiority}} = \frac{1}{2} \times \left(\frac{1.96 + 0.845}{\arcsin \sqrt{0.40} - \arcsin \sqrt{0.58}} \right)^2 = 121$$

However, we are assuming that lost to follow up or refuse to include in trial will be 20%, that means 24. So at least 150 patients will be allocated randomly and power of this study will be 80%.

Allocation:

Randomized: Block randomization (Computer generated randomization code)

Intervention model: Parallel assignment

Intervention model description: Patient will be randomized 1:1 to placebo with standard care and combined doxycycline and ivermectin with standard care.

Blinding: Double blind (The participant and the clinicians/data collectors will be unaware of the treatment the participant receives)

Primary purpose: Treatment

Official title: A phase III trial to promote recovery from covid 19 with combined Doxycycline and Ivermectin along standard care.

Provider of placebo and active ingredients: Popular pharmaceutical limited

Dosage of the drugs: Ivermectin 6 mg 2 tab stat, cap Doxycycline 100 mg 1 cap BD 5 days

Content of the placebo:

Placebo description of Ivermectin: Attached with Annexure 1

Product Name: Placebo Tablet of Ivec 6 Tablet

Batch No.: PB029

Mfg. Date: JUN 2020

Exp. Date: MAY 2022

Appearance: A pale yellow colored, round, standard bi-convex uncoated tablet with a bre line on one side and other side plain

Composition:

SL. No.	MATERIAL NAME	QUANTITY PER TABLET	PERCENTAGE PER TABLET
1.	Microcrystalline Cellulose (PH102)	63.355 mg	74.544 %
2.	Pregelatinised Starch (Starch 1000)	20.000 mg	16.500 %
3.	Sodium Starch Glycolate (Type A)	9.375 mg	7.500 %
4.	Anhydrous Citric Acid	0.013 mg	0.010 %
5.	Butylated Hydroxyanisol (BHA)	0.012 mg	0.010 %
6.	Pigment Blend Yellow PB0071	0.045 mg	0.036 %
7.	Colloidal Anhydrous Silica (Aerosil 200)	0.500 mg	0.400 %
8.	Magnesium Stearate	1.750 mg	1.400 %

Placebo Description of Doxycycline: Attached with Annexure II

Product Name: Placebo Capsule of Doxibac 100 Capsule

Batch No.: PB030

Mfg. Date: JUN 2020

Exp. Date: MAY 2023

Appearance: Hard gelatin capsule shell size #2 having white opaque body imprinted with popular logo in black ink and dark blue opaque cap containing white granular powder

Composition:

SL. No.	MATERIAL NAME	QUANTITY PER CAPSULE	PERCENTAGE PER CAPSULE
1.	Anhydrous Lactose	247.650 mg	88.440%
2.	Microcrystalline Cellulose (PH102)	7.350 mg	2.626%
3.	Sodium Starch Glycolate (Type A)	20.000 mg	7.143%
4.	Magnesium Stearate	5.000 mg	1.766%
5.	EHGC Shell Size #2 (Body: White Opaque, Cap: Dark Blue Opaque)	1 Pc.	---

Estimated study date: 01 June, 2020

Estimated primary completion date, 25 August 2020

Estimated study completion date: September, 2020

Inclusion Criteria:

- At least 18 years of age
- COVID-19 infection, confirmed by polymerase chain reaction (PCR) test within 3 days from enrollment
- Only mild and moderate COVID-19 infected cases
- Able to provide informed consent

Exclusion Criteria:

- Unable to take oral medication
- Pregnant or breast feeding lady
- Patients with severe COVID symptoms or admission in ICU/HDU

- Alanine Aminotransferase (ALT) or aspartate aminotransferase (AST) > 5 X upper limit of normal (ULN)
- On non-invasive positive pressure ventilation or mechanical ventilation at time of study entry
- Known hypersensitivity to Doxycycline or ivermectin or its components.

Research instruments:

1. Informed consent form.
2. Case record form

Primary Outcome Measure:

The number of days required for clinical improvement

1. Early Clinical improvement of the patients
How many days it requires to become the patient completely symptoms free
[Time Frame: 7 days]
2. Late clinical recovery
How many days the symptoms persist
[Time Frame: 12 days]

Secondary Outcome Measure:

1. Percentage of patients having clinical deterioration.
Patients deteriorating to next level of severity, like moderate, severe and death
[Time Frame: 1 month]
2. Persistently positive for RT-PCR.
Percentage of Covid-19 Patients repeatedly become positive for RT-PCR for Covid-19
[Time Frame: 14 days]

Data collection technique:

Data will be collected by assigned. trained data collectors (Physician).

Patient will be enrolled according to defined inclusion and exclusion criteria in the current research. Informed written consent will be obtained from the patient or their relatives. Each patient participating in the trial will be uniquely identified, and information such as his name, address is recorded in the trial 'subject number list'. Only the principle investigator will be aware about the allocation of the drugs. The patients

and the data collectors will be unaware about the group allocation of the drugs. The Data will be reviewed by the co-investigators. It will be managed by principle and co-principle investigators in designated computer.

Clinical assessment (fever, cough, Anorexia, Temperature, pulse, blood pressure, respiratory rate, oxygen saturation) will be done every day. Routine investigation (CBC, ESR, CRP, Creatinine, RBS, SGPT, chest x-ray, D- Dimer) will be done at admission and at day 3, 5, 7, 10 and 14 day. In case of the clinical deterioration it would done according to necessity. RT-PCR will be done at day-0, Day 5, day 7 and day 14.

Standard care: both the experimental and placebo will receive the available standard of care, like-

- Paracetamol, Antihistamine, Cough suppressant, Vitamins
- Oxygen therapy according to indication and need
- Low molecular weight heparin according to indication
- Appropriate other broad spectrum antibiotics
- Other drugs for associated co- morbid condition

Management of the adverse events:

Drugs adverse effect will be monitored by a defined committee. The patient experiencing adverse effect of the drugs will be discontinued from the study. It will be managed with priority to the highest possible level by the hospital authority as well as the investigators.

If the patient progresses from mild to moderate or severe disease, the study will be continued and available management of the appropriate severity will be immediately started. The patient will be monitored closely.

Data analysis:

Data will be analyzed by computer with the help of SPSS (Statistical Package for Social Sciences) version 20. To compare mean of the two group chi square will be used. Comparing drug outcome in between two group survival analysis by Kaplan-Meier curve will be done for the duration of recovery. Odds ratio will be formulated from linear logistic regression for early and late clinical recovery. Hazard ratio will be formulated from the cox regression analysis for severity conversion and persistence of the positivity. Crude odds ratio will be adjusted in cox proportional hazard ratio model. Each Ivermectin-Doxycycline plus standard of care group will be compared with the placebo plus standard care group using the log-rank test, hazard ratio and 95% CI. Participants who were lost to follow up, died, discontinue drugs due to adverse effect will censored on the last study day. All P values will be two-sided and will be shown without

adjustment for multiple testing. All analyses will be performed according to the intention to treat principle.

Dropout management: Intention to treat measure will be taken

Observation and Results:

Result of the study and statistical analysis will be presented by tables, figures, graphs, diagrams, charts and photographs. All these would have own legends (i.e. title) and will be serially numbered.

Discussion:

Discussion will be done on the basis of result obtained from the study and comparing with similar studies done at home and abroad.

Summary:

Summarization will be drawn after discussion.

Conclusion:

Conclusion would be drawn depending upon the results and discussion

Conflict of interest:

Popular pharmaceutical will only provide drugs and the placebo.
None of the investigators will receive remuneration from the pharmaceutical company.
They will not get any access to data profile.

Operational definition:

(According to WHO guideline)

Confirmed Covid-19:

Cases with positive RT-PCR for Covid 19 irrespective of symptoms.

Uncomplicated (mild) Illness

These patients usually present with symptoms of an upper respiratory tract viral infection, including mild fever, cough (dry), sore throat, nasal congestion, malaise, headache, muscle pain, or malaise. Signs and symptoms of a more serious disease, such as dyspnea, are not present.

Moderate Pneumonia

Respiratory symptoms such as cough and shortness of breath (or tachypnea in children) are present without signs of severe pneumonia.

Severe Pneumonia

Fever is associated with severe dyspnea, respiratory distress, tachypnea (> 30 breaths/min), and hypoxia ($\text{SpO}_2 < 90\%$ on room air). However, the fever symptom must be interpreted carefully as even in severe forms of the disease, it can be moderate or even absent. Cyanosis can occur in children. In this definition, the diagnosis is clinical, and radiologic imaging is used for excluding complications.

Acute Respiratory Distress Syndrome (ARDS)

The diagnosis requires clinical and ventilatory criteria. This syndrome is suggestive of a serious new-onset respiratory failure or for worsening of an already identified respiratory picture. Different forms of ARDS are distinguished based on the degree of hypoxia. The reference parameter is the $\text{PaO}_2/\text{FiO}_2$:

- Mild ARDS: $200 \text{ mmHg} < \text{PaO}_2/\text{FiO}_2 \leq 300 \text{ mmHg}$. In not-ventilated patients or in those managed through non-invasive ventilation (NIV) by using positive end-expiratory pressure (PEEP) or a continuous positive airway pressure (CPAP) $\geq 5 \text{ cmH}_2\text{O}$.
- Moderate ARDS: $100 \text{ mmHg} < \text{PaO}_2/\text{FiO}_2 \leq 200 \text{ mmHg}$.
- Severe ARDS: $\text{PaO}_2/\text{FiO}_2 \leq 100 \text{ mmHg}$.

When PaO_2 is not available, a ratio $\text{SpO}_2/\text{FiO}_2 \leq 315$ is suggestive of ARDS.

Chest imaging utilized includes chest radiograph, CT scan, or lung ultrasound demonstrating bilateral opacities (lung infiltrates $> 50\%$), not fully explained by effusions, lobar, or lung collapse.

Clinical improvement Criteria

1. Body temperature remains normal for at least 3 days (ear temperature is lower than 37.5°C).

2. Respiratory symptoms are significantly improved.
3. Lung imaging shows obvious improvement in lesions.
4. There is no co-morbidities or complications which require hospitalization.
5. SpO₂, >93% without assisted oxygen inhalation.

8. FLOW CHART of Study workup:

Sl No	Activities						
		1 st	2 nd	3 rd	4 th	5 th , 6 th , 7 th	8 th
1	Recruitment and training of the field staff						
2	Pretesting and finalization of the questionnaire						
3	Consultative meeting						
4	Data collection						
5	Data entry and editing						
6	Data analysis and draft report writing						
7	Dissemination of Results						

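### The protocol's 80% power belongs to about 150 patients per group after 20% loss, not to the planned 200 per group, which has about 90% to 95%

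*Protocol*

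**What the plan says.** Section 4 (Methodology) of the protocol opens with the planned size: "Estimated enrollment: 200 participants per group". The project summary before Part D agrees: "The study would be conducted on 200 confirmed cases of Covid- 19. Another 200 patients will receive placebo". Allocation is 1:1.

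The calculation in section 4 uses an arcsine formula for two proportions and defines "N=size per group". The assumed values are 0.40 for standard treatment, 0.58 for the new treatment, alpha 0.05 and beta 0.20. The list also holds a difference of 0.18 and a margin of 0.10. The result is 121, and its label is statistical superiority.

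An allowance follows: "However, we are assuming that lost to follow up or refuse to include in trial will be 20%, that means 24". The conclusion is "So at least 150 patients will be allocated randomly and power of this study will be 80" per cent.

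The Data analysis section confirms the sidedness: "All P values will be two-sided". The primary outcome is a number of days to clinical improvement, with 7-day and 12-day frames. Data analysis plans Kaplan-Meier curves and a log-rank comparison, and odds ratios from logistic regression for early and late recovery.

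**The concern.** Sample size and power tell a reader when recruitment is complete and what a null result would mean. Here two sizes stand in one section with nothing to link them. The floor of 150 has no unit. The only power printed is attached to that floor and called the power of the study, while the planned enrolment has none. A reader cannot tell from the text whether stopping at 150 per group, or at 150 altogether, would satisfy the plan.

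The steps between 121 and 150 do not hold together either. Adding 20% of the required number does not protect against losing 20% of those randomised. The 150 follows neither from that addition nor from the correct division. The allowance mixes refusal with loss to follow-up, although a refusal before randomisation takes nobody out of the randomised groups. The 0.10 margin, the symbols that go with it and a pooled standard deviation are introduced but have no place in the formula used. Finally, the response rates that drive the size are not tied to the days-to-improvement outcome or to a day.

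**Working it through.** **Inputs** (all from section 4 unless noted): rates 0.40 and 0.58; z = 1.96 (two-sided 5%, confirmed in Data analysis); z = 0.845 (80% power); 20% loss; 200 per group (also in the project summary).

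**1. The protocol's own figure.** The arcsine difference is arcsin√0.58 − arcsin√0.40 = 0.18102. Then

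N = ½ × ((1.96 + 0.845) / 0.18102)² = 120.05,

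which rounds up to 121 per group. The stated figure reproduces. The pooled-proportions formula gives 120.

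**2. The loss allowance.** The protocol takes 0.20 × 121 = 24.2, written as 24. To keep 121 after losing 20%, the number randomised must be 121 / (1 − 0.20) = 151.25, so 152 per group. The stated 150, read per group, leaves 150 × 0.8 = 120, against the unrounded requirement of 120.05. The gap to 152 is two patients per group.

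**3. Power for each reading.** With n evaluable per group,

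power = Φ(√(2n) × 0.18102 − 1.96).

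| Reading | Evaluable per group | Power |
|---|---|---|
| 150 per group, 20% loss | 120 | 80.1% |
| 150 per group, no loss | 150 | 88.0% |
| 200 per group, 20% loss | 160 | 89.9% |
| 200 per group, no loss | 200 | 95.2% |
| 150 in total, no loss | 75 | 60.1% |
| 150 in total, 20% loss | 60 | 50.9% |

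For the planned 200, for example: √400 × 0.18102 − 1.96 = 1.660, and Φ(1.660) = 95.2%. A normal-approximation test of two proportions agrees within half a point in every row.

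**4. The margin.** The formula in step 1 contains only the two rates and the two normal deviates. Setting the margin to any other value leaves N unchanged, so the 0.10 plays no part in the 121.

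**The case against.** The defence is strong on several counts, and most of it stands.

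- **A floor is not a contradiction.** Read per group, 150 is a minimum that 200 exceeds, and 80% is the right power for it after 20% loss. That stands. What remains is that the sentence calls 80% the power of the study, while the study planned is larger.
- **150 as a total.** A reader might infer that the trial may stop at 75 per group, with 51% to 60% power. The text does not favour this. N is defined per group, 150 follows directly from a per-group 121, and both enrolment statements give 200 per group. A total of 150 would also fall below the requirement just calculated. The missing unit is a wording gap, not evidence of an underpowered trial.
- **The additive allowance.** A reader might add 121 and 24, get 145, and conclude that the trial falls short. The protocol prints no 145. It goes to 150, which is almost the correct 152, so the slip does no numerical harm.
- **The margin.** A reader might take the 0.10 as a claim of benefit beyond 10 percentage points. No objective or analysis in the protocol makes that claim, and the result is labelled as statistical superiority. The margin is an unused leftover.
- **Binary rates.** A response rate is not foreign to the plan, because logistic regression for early and late recovery is foreseen. That is fair, but the protocol still does not say which of these, if either, the 40% and 58% describe.

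**Conclusion.** The point holds as an inconsistency of statement. The planned 200 per group has about 90% power after the protocol's own 20% loss and about 95% without loss. The printed 80% understates this by roughly 10 to 15 percentage points, and it is correct only for about 150 per group after loss. The error is on the safe side: under its stated assumptions the trial is large enough. Neither the additive allowance nor the unused margin makes the 80% wrong; the mismatch comes only from planning 200 per group without restating the power.

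The figures rest on 40% versus 58%, two-sided 5%, 1:1 allocation, and patients who are lost contributing nothing to a comparison of proportions. They say nothing about the power of the log-rank test on days to improvement. That would need a time point for the two rates and a shape for the recovery curve, and the protocol gives neither. Severity is minor to moderate.

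**What to change.** Text changes in section 4, with no extra patients and no change to the design:

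1. State one size everywhere: 200 per group, 400 in total. Give its power for 40% versus 58% at two-sided 5%: about 90% if 20% are lost after randomisation, about 95% with complete data.
2. Replace the sentence on 150 with a minimum of 152 per group, shown as 121/0.8, for 80% power after 20% loss; or delete it.
3. Limit the 20% allowance to loss after randomisation, and take refusals out of it.
4. Delete the 0.10 margin, its symbols and the pooled standard deviation, because only statistical superiority is tested.
5. Have the sponsor state which outcome and which day the 40% and 58% refer to, and how they relate to the primary outcome. Day 7 should not be written in by assumption.
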